1.5.1 Potential benefits

There will be no direct benefit to the subjects from the participation in the study. The knowledge gained from this study will help to define optimal grafting protocols, and therefore be a benefit to society.

2 Study Objectives

Primary Objective

To determine the effects of small and large bone graft particles vs large particles alone on percent vital bone, percent residual graft material, and bone graft volume, measured histologically from bone biopsies of the grafted site taken at the time of dental implant placement from subjects undergoing sinus augmentation for the placement of dental implants

Secondary Objective

To observe clinical and radiographic bone gain in order to calculate bone volume differences between conditions and the implant survivability.

3 Study Design

3.1 General Design

The proposed study is a Randomized, single-masked, split-mouth, single center study.

About 20 subjects will be screened in order to randomize 10 study subjects. 10 patients who needing bilateral sinus augmentation procedure using the lateral window technique will be randomized using computer generated randomized technique.

Pre-surgical Plan:

All procedures below are standard of care. Cone beam computed tomography (CBCT) scans are obtained for each patient (NYUCD radiology department). Standardization was done for the radiographic evaluations and measurements are for each patient is made using a radiographic guide. In cases of abnormal thickening of the membrane, suspected cysts or tumors in the sinus, patients are referred to an otolaryngologist (ENT). All patients are prescribed antibiotic and Flonase to be initiated one hour prior to the surgery (Augmentin 875 mg two times a day for 10 days; or ciprofloxacin 500 mg two times a day for 10 days in case of penicillin allergy) in order to minimize risk of infection and to control postoperative discomfort.

Surgical Procedure:

The sinus augmentation procedure is standard of care.

The use of different size and type (cortical or cancellous) of bone graft material for the two sites in order to evaluate the difference in outcome (if any), is for research purposes.

On the day of the surgical procedure, patients are instructed to rinse with chlorhexidine digluconate 0.12% (Peridex) solution for 30 seconds. Betadine is applied over three quarters of their faces prior to the initiation of the surgery. The procedure is performed under local anesthetic: 2% lidocaine with 1:100,000 epinephrine. A full thickness flap is elevated over the buccal aspect, exposing the lateral wall of the maxillary sinus. An oval-shaped osteotomy is constructed on the lateral surface of the sinus wall using Piezo with sterile saline irrigation. Using specialized curettes, the Schneiderian membrane is carefully elevated and gradually detached along the inferior wall to the medial-anterior walls and extended posteriorly until sufficient space is made for future implant placement. A mixture of 25% small-particle cortical allograft, 25% large-particle cortical allograft, 25% small-particle cancellous allograft, and 25% large-particle cancellous allograft is used for one sinus (Zimmer Biomet). The contralateral sinus will have 100% large particle cancellous allograft (Zimmer Biomet). The allografts are hydrated in sterile saline solution and packed using little pressure from the anterior to the posterior part of the sinus cavity. A resorbable Pericardium membrane (Puros CopiOs pericardium, Zimmer Biomet) is extended at least 3mm beyond the limits of the lateral window. Primary closure of the flap is achieved using 4.0 vicryl sutures. Provisional fixed or removable appliances are relieved over the edentulous areas before reinsertion.

CONFIDENTIAL

This material is the property of the NYU College of Dentistry. Do not disclose or use except as authorized in writing by the study sponsor

Post-operative Care and Follow-Up:

All procedures below are standard of care. All patients are provided with verbal and written post-operative instructions following the sinus augmentation procedure. Patients are instructed to continue the antibiotic regime for a total of 14 days and to take Tylenol ES or Ibuprofen 800 mg, or a combination of both staggered as needed for pain management. Patients are seen for evaluation one week after the surgery. Sutures are removed at a two-week follow-up visit. Thereafter, patients return for follow-up visits at 1, 3, and 6 months post-operatively. If the contralateral sinus augmentation procedure was not done at the same time, it will be done no later than 6 weeks following the first surgery.

Bone Core Harvesting and Implant placement:

After 8 months, a post-operative CBCT is taken as part of standard of care in order to determine the bone gain. The CBCT will be taken as one full maxillary arch in case the two sinuses were done at the same time of surgery or as a separate sectional in case they were done apart but always for each at the six month mark. Dental implant placement is completed under local anesthesia. In case of severe anxiety, implants can be placed while patients are under conscious sedation. A crestal incision is made and a full-thickness envelope flap is elevated. A surgical guide is used for both core harvesting (Research purposes) and implant placement. Using a trephine bur similar in width to the 2.5mm pilot drill, a bone core of at least 5mm long is harvested from inside the grafted sinus. Following core harvesting, the bone cavity is further prepared for a dental implant (Zimmer Biomet Trabecular Metal Dental Implant) and the implant is placed according to the manufacturer's recommendations (Standard of care).

The harvested bone core will be fixed in 10% buffered formalin for 10 to 12 hours and cut into thinly ground longitudinal sections using a precision cutting instrument (Microtome; Nanjing Everich Medicare Import & Export, Co., Ltd, Nanjing, China). The specimens will be dehydrated in an ascending series of alcohol rinses and embedded in a glycolmethacrylate resin (Technovit 7200 VLC; Kulzer, Wehrheim, Germany). After polymerization, specimens are longitudinally cut into 150-mm-thick sections with a high-precision diamond disc and then ground down to about 30 mm in thickness with a specially designed grinding machine. The resulting slides are stained with hematoxylin and eosin and sent to the pathology department at NYUCD for histologic analysis. Quantitative histomorphometry is accomplished using software (OsteoMeasure; OsteoMetrics, Inc., Atlanta, GA), which interfaces with a light fluorescence microscope (eg, Olympus TIRFM; Olympus Corporation, Tokyo, Japan) and digital camera (eg, Olympus Microfire; Olympus Corporation). Quantitative histology of hematoxylin and eosin-stained slide sections are assessed according to the methods of Parfitt et al for various histology features and scored using a stratified 5-point scale and a simplified 2-point scale that collapsed findings into 2 broad categories for clinical relevance.

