1.5 Research Risks & Benefits

The products used in the present study are FDA approved for this purpose, and have well documented safety profiles, therefore we anticipate minimal risk to study subjects due to the graft materials used. Both sizes of graft material are used for sinus augmentation procedures at the discretion of dentists, outside of this study. To date there are no specific guidelines as to which particle size is more favorable and therefore should be exclusively used for the sinus augmentation procedures. The risks associated with randomization are one size graft site may have a different outcome than the other size graft site.

Other risks related to the sinus augmentation procedure, implant placement and follow up evaluations are the following:

Local anesthesia: Although adverse reactions are rare, they may include numbness for an extended amount of time, pain, discomfort and bruising. Even more rarely, infections may be caused by the administration with the local anesthetic. (Standard of Care)

Sinus augmentation procedure: The procedure itself called lateral window approach, will entail an elevation for an extended gingival flap for access, osteotomy in the lateral maxillary wall of the sinus and elevation of the Schneiderian membrane. Risks of perforation of the membrane are evaluated at 20% and depends on the extent of them, might require to abort the procedure and come back in 4 months to re-elevate requiring the patient to go through twice of the same procedure. There is also a risk of post-operative infection, some nasal bleeding or intra-operative bleeding and pain which all can be controlled. The patients will be placed on antibiotic for 14 days as a precautionary procedure starting one day before and continuing till finishing the prescribed dose. (Standard of Care)

X-rays:

All the intraoral x-rays are standard of care.

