6.1 Screening Visit (Day 0)

Subjects are patients assigned to graduate students within the Program for Advanced Education in Periodontics, an approved program of graduate study within the College of Dentistry. Subjects requiring sinus augmentation and implant placement and who agree to a treatment plan consisting of sinus augmentation and implant placement will be considered for enrollment. Subjects will be screened for eligibility during their clinical care appointment, and if deemed eligible, will be asked by their Graduate student if they are willing to participate in the clinical study. Subjects that meet inclusion and exclusion criteria and sign an approved study informed consent form will be scheduled for sinus augmentation surgery.

Cone beam computed tomography (CBCT) scans are obtained for each patient (NYUCD radiology department). Standardization for the radiographic evaluations and measurements for each patient is made using a radiographic guide. In cases of abnormal thickening of the membrane, suspected cysts or tumors in the sinus, patients are referred to an otolaryngologist (ENT) for consultation and or treatment prior to consideration for sinus augmentation. All patients are prescribed antibiotic and Flonase to be initiated one hour prior to the surgery (Augmentin 875 mg three times a day for 7 days; or ciprofloxacin 500 mg two times a day for 7 days in case of penicillin allergy) in order to minimize risk of infection and to control postoperative discomfort as per standard of care.

- Obtain informed consent of potential participant verified by signature on written informed consent form (Research purposes)
- Obtain demographic information, alcohol and tobacco use history
- Screen potential subjects by inclusion and exclusion criteria (Research purposes)
- Obtain and review medical/dental history, and concomitant medications
- Record blood pressure and pulse
- Standardized peri-apical radiographs, if needed
- Oral examination
- Alginate impressions taken for study model, wax-up, and radiographic/surgical template fabrication if not done prior to the screening visit
- Cone beam computed tomography with radiographic template (if not performed within 12 months prior to screening visit)
- Radiographic/surgical stent fabrication if not done prior to the screening visit
- Provide participants with prescriptions and specific instructions needed to prepare for first study visit

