- Review medical and dental history, and concomitant medications
- Record blood pressure and pulse
- Oral examination
- Local anesthesia administration
- Flap reflection
- Randomization (Research purposes)
- Sinus augmentation surgery (*if possible both sinus augmentation surgery will be performed on the same visit) (Research purposes)
- CBCT immediately after the surgery (Research purposes)
- Oral photographs
- Record adverse events: Subject will be contacted by phone within 24 hours from the surgery: During that conversation, they will be asked if they are experiencing any discomfort, oozing or bleeding, pain, discomfort, numbness of the lip. If anything sounded suspicious, they will be asked to come in for an evaluation.

6.3 Visit 2 (1 week ± 2 days) 1 week Follow-up assessments of study and safety

- Review medical and dental history, and concomitant medications
- Record adverse events as reported by participant or observed by investigator (Research purposes)
- Oral examination and evaluation of the surgical area
- Assessment of the healing process
- Documentation of any possible complications
- Standardized peri-apical radiographs, if needed
- Oral photographs

All patients are provided with verbal and written post-operative instructions following the sinus augmentation procedure. Patients are instructed to continue the antibiotic regime for a total of 14 days and to take Ibuprofen 800 mg as needed for pain management. Patients are seen for evaluation one week after the surgery. Sinus augmentation on the contralateral side is done no later than 6 weeks following the first surgery.

6.4 Visit 3 (2 week ± 2 days) 2 week follow-up assessments of study and safety

Sutures are removed at a two-week follow-up visit.

- Review medical and dental history, and concomitant medications
- Oral examination
- Record adverse events as reported by participant or observed by investigator (Research purposes)
- Removal of sutures
- Standardized peri-apical radiograph, if needed
- Oral photographs

CONFIDENTIAL

This material is the property of the NYU College of Dentistry. Do not disclose or use except as authorized in writing by the study sponsor

6.5 Visit 4 (4 weeks \pm 7 days) Possible Sinus Augmentation of contralateral sinus (*This visit is only done if the Sinus Augmentation of contralateral sinus was NOT performed during visit 1)

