6.8 Visit 5 (7 month \pm 2 weeks) Pre-implant placement Visit and CBCT

Prior to the implant placement, a post-operative CBCT is taken as part of standard of care in order to determine the clinical outcome of the sinus augmentation bone graft and the clinical situation.

CONFIDENTIAL

This material is the property of the NYU College of Dentistry. Do not disclose or use except as authorized in writing by the study sponsor

- Review medical and dental history, and concomitant medications
- Record blood pressure and pulse
- Record adverse events as reported by participant or observed by investigator (Research purposes)
- Oral examination and evaluation of the surgical area
- Assessment of the healing process
- Documentation of any possible complications
- Standardized peri-apical radiographs, if needed
- Oral photographs
- CBCT
- CBCT review to determine the clinical outcome and the type of implant to be ordered
- Order of implants
- Provide participants with prescriptions and specific instructions needed to prepare for implant surgery

6.9 Visit 6 (8 month \pm 7 days) Implant placement and bone core collection from both sinuses

Patients are instructed to rinse with chlorhexidine digluconate 0.12% (Peridex) solution for 30 seconds. Betadine is applied over three quarters of their faces prior to the initiation of the surgery. The procedure is performed under local anesthesia: 2% lidocaine with 1:100,000 epinephrine. In case of severe anxiety, implants can be placed while patients are under conscious sedation. A crestal incision is made and a full-thickness envelope flap is elevated. A surgical guide is used for both core harvesting and implant placement. Using a trephine bur similar in width to the 2.5mm pilot drill, a bone core of at least 5mm long is harvested from inside the grafted sinus (Research purposes). Following core harvesting, the bone cavity is further prepared for a dental implant (Zimmer Biomet Trabecular Metal Dental Implant) and the implant is placed according to the manufacturer's recommendations.

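### The antibiotic instructions for sinus augmentation contradict each other on frequency, duration and start; follow-up visits and core and CBCT times also need reconciling

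*Combined protocol and SAP*

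**What the plan says.** **Antibiotic for sinus augmentation.**
- Section 3.1, pre-surgical plan: "Augmentin 875 mg two times a day for 10 days", or ciprofloxacin 500 mg twice daily for 10 days in penicillin allergy. On the start: "All patients are prescribed antibiotic and Flonase to be initiated one hour prior to the surgery".
- Sections 6.1 and 6.2: "Augmentin 875 mg three times a day for 7 days", or ciprofloxacin 500 mg twice daily for 7 days, again starting one hour before surgery.
- Section 1.5: "The patients will be placed on antibiotic for 14 days as a precautionary procedure starting one day before".
- Section 3.1, post-operative care: "Patients are instructed to continue the antibiotic regime for a total of 14 days". Section 6.3 (Visit 2) repeats the instruction to "continue the antibiotic regime for a total of 14 days".

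**Visits.** Section 3.1 has patients return at 1, 3 and 6 months. Section 6 and Attachment A schedule no 3- or 6-month visit. Visits 4, 4A and 4B (weeks 4 to 6) apply only when the second sinus is operated on separately.

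**Core and CBCT times.** Section 5.2 puts core harvest at 6 months, Section 6.9 at 8 months ± 7 days. The post-graft CBCT is at 8 months in Sections 1.5, 3.1 and 3.3. It is at six months for each sinus in the next sentence of Section 3.1, and at 7 months ± 2 weeks in Section 6.8.

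**The concern.** The antibiotic statements all stand in current text and concern the same operation, so a clinician who follows one section departs from another. The protocol does not leave the regimen to the clinician's judgement: it writes out drug, strength, frequency, start and length. Section 8.3.1 requires sponsor and IRB approval before any deviation.

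The protocol itself treats the matter as one of safety. Section 3.1 gives infection control as a purpose of the antibiotic, Section 5.4 calls the first month the most sensitive period, and Section 1.5 lists antibiotic side effects, up to anaphylaxis, among the risks to subjects.

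The other two items are smaller. Staff cannot tell whether the 3- and 6-month visits are required. The core and CBCT times set how much healing has taken place when vital bone and volume change are measured.

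**Working it through.** The plan states no summary figure to reproduce. The check compares the passages and applies simple arithmetic.

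**1. Antibiotic**

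| Section | Augmentin 875 mg | Ciprofloxacin 500 mg | Duration | Start before surgery |
|---|---|---|---|---|
| 3.1 pre-surgical | twice daily | twice daily | 10 days | one hour |
| 6.1, 6.2 | three times daily | twice daily | 7 days | one hour |
| 1.5 | not stated | not stated | 14 days | one day |
| 3.1 post-operative, 6.3 | not stated | not stated | 14 days in total | not stated |

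- Daily Augmentin: 2 × 875 = 1,750 mg; 3 × 875 = 2,625 mg; ratio 2,625 / 1,750 = 1.50.
- Doses in the course as written: 2 × 10 = 20; 3 × 7 = 21. In mg: 20 × 875 = 17,500; 21 × 875 = 18,375; ratio 1.05.
- If both were extended to 14 days: 2 × 14 = 28 against 3 × 14 = 42 doses.
- Daily ciprofloxacin: 2 × 500 = 1,000 mg in both versions; only the duration differs (10 or 7 days).

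**2. Visits** (one month = 365.25 / 12 = 30.44 days)

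If Section 6 governs, a subject with both sinuses done on the same day goes from Visit 3 (day 14 ± 2) to Visit 5 (7 months = 213.1 days, ± 14).
- Nominal gap: 213.1 − 14 = 199 days.
- Shortest: (213.1 − 14) − (14 + 2) = 183 days.
- Longest: (213.1 + 14) − (14 − 2) = 215 days.

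The 24-hour call, the week-1 and week-2 visits and unscheduled visits (Section 6.13) remain.

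**3. Core and CBCT times**

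- Core: 8 months − 6 months = 243.5 − 182.6 = 61 days between the two stated times.
- CBCT: the Visit 5 window is 213.1 ± 14 = days 199 to 227. Six months (day 183) falls 16 days before it opens, for same-day subjects and for the first sinus of staged subjects.
- Staged subjects: the second surgery is at 28 ± 7 = 21 to 35 days after the first (Section 6.5), or up to 6 × 7 = 42 days (Sections 3.1 and 6.3). Both cores are taken at one Visit 6, so healing differs between the sinuses by that amount.
- With Visit 6 counted from the first surgery, the second sinus has 243.5 − 28 = 215.5 days, or 7.1 months, against 8.0 for the first. At lags of 21, 35 and 42 days the figures are 7.3, 6.9 and 6.6 months.
- Same-day subjects have equal healing on both sides whichever time applies.

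**The case against.** The best defence is that the 14-day sentences in Sections 3.1 and 6.3 simply extend the first course. That reading is possible, and Section 1.5 states a 14-day course outright. It would settle the total length, but not twice against three times daily, a written course of 10 against 7 days, or one hour against one day.

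It is also fair to say that the antibiotic is standard of care (Section 5.5), that no endpoint depends on it, and that the two courses are nearly equal in total. All of that stands. It limits the consequence but does not remove the contradiction.

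A reader might infer several stronger things that the documents do not support:
- *The supply runs out before day 14.* The Section 6 task lists have "Provide participants with prescriptions and specific instructions needed to prepare for first study visit" and next "Provide participants with prescriptions and specific instructions needed to prepare for implant surgery", with no prescription item at Visit 2. But the Visit 1 list has none either, although the text of Section 6.2 says antibiotics are prescribed. An empty list therefore shows nothing about renewal.
- *Same-day subjects go unseen for over six months.* The 199 days hold only if Section 6 overrides Section 3.1, and the 1-, 3- and 6-month visits may be routine clinic care.
- *The clock is unstated.* Section 6.6 places Visit 4A both at 5 weeks and one week after the second surgery, so Section 6 counts from the first surgery. The conflict is with Section 3.1, which times the CBCT for each sinus.
- *The 8-month CBCT lies a known distance after the Visit 5 window.* The column marks in Attachment A look displaced in the available copy, so no figure is given for that gap.

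**Conclusion.** The antibiotic contradiction is real and wrong as written. Augmentin is 1,750 or 2,625 mg per day, the duration of either drug is 7, 10 or 14 days, and the start is one hour or one day before surgery. No reading makes all the sections agree. The need for correction rests on this item alone.

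The visit conflict is minor; its size, about 199 days (183 to 215), is conditional on Section 6 governing. The core and CBCT conflict is also minor. The stated core times are about 61 days apart, and in staged subjects the two sinuses differ by 21 to 35 days of healing at the single core visit, or up to 42 by the six-week limit.

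It would be tempting to conclude that the paired comparison is biased. The documents do not support that. Same-day subjects heal equally on both sides, the randomization table assigns grafts to right or left (Section 6.2), and no direction of bias follows. Nor is any effect of the antibiotic on the graft comparison claimed.

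**What to change.** The sponsor and the investigator must reconcile Sections 1.5, 3.1, 3.3, 5.2, 6.1 to 6.9 and Attachment A so that they agree on:
- antibiotic frequency, start and duration for sinus augmentation, including whether the 14-day total extends the first course;
- the post-operative visit list, for same-day and for staged subjects;
- the core and CBCT times, with the reference surgery named for staged subjects.

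Which regimen, visits or times to adopt is for them to decide.

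In the analysis, report the graft-to-core and graft-to-CBCT interval for each sinus, derived from the surgery and visit dates already recorded.

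The cost is a text amendment and a short derived listing, with no added subjects. Whether any visit is added or dropped depends on how Section 3.1 and Section 6 are reconciled.
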